7.6 Immunogenicity

Assessments of anti-drug antibodies (ADA) will be performed at pre-dose at Month 1, Month 2, Month 4, Month 7, Month 13, and Month 18 as specified in [Section 10.2 “Trial Assessments”](#). The pre-dose sample taken at Month 1 will be considered the serum sample taken prior to dosing of avacincaptad pegol for Sham patients crossing over to avacincaptad pegol to capture a drug-free baseline.

Two serum samples of 2 mL will be collected at each timepoint specified: one for primary analysis and one as a back-up.

The Sponsor may request ad-hoc ADA sampling in the event of an adverse drug reaction.

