7.7 Pharmacokinetics

The concentration of avacincaptad pegol in K₂EDTA human plasma samples will be quantified using validated electrochemiluminescence dual hybridization assay and expressed in terms of ng/mL. Plasma PK samples will be collected at pre-dose at Month 1 (baseline), Month 2, Month 4, Month 7, Month 13, and Month 18 as specified in [Section 10.2 “Trial Assessments”](#) prior to administration of avacincaptad pegol in order to evaluate the effect of ADA on the plasma concentrations of avacincaptad pegol.

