4.4 Secondary Endpoint(s) Analysis

The secondary endpoints include immunogenicity and pharmacokinetics. All the assessments will be mapped to an analysis visit. The mapping rule is provided in Table 4.

Immunogenicity

ADA status (either positive or negative) will be evaluated by ADA against ACP, ADA against aptamer and ADA against Polyethylene glycol (PEG) for each ADA sample.

The following ADA incidences will be summarized over the ADAAS in total. A listing of ADA results will also be provided. Baseline value is the last available value prior to the first administration of study drug in this study ISEE2009.

Table 1 Definition of the ADA Incidences

ADA Incidence	Definition
Baseline and at least one post-baseline status	Number of participants with valid baseline and at least one post-baseline ADA results
Baseline negative	Number of participants with a negative ADA status at baseline
Post-baseline positive, who were negative at baseline	Number of participants with a negative baseline and at least one positive post-baseline ADA status
Baseline positive	Number of participants with a positive ADA status at baseline
Post-baseline positive	Number of participants with at least one post-baseline positive ADA status
Treatment boosted positive	Number of participants with an at least one post-baseline ADA increase from a positive baseline ^a
Total Positive	Total number of participants who are either with a negative baseline and at least one post-baseline positive ADA status, OR treatment boosted positive
Total Negative	Total number of participants who are not total positive
^a For participants with positive baseline ADA status, a post-baseline titer value that is ≥ 4 times higher than the baseline is considered as treatment-boosted ADA.	

A plot of plasma concentrations vs. analysis visits (months) will be created. Plasma concentrations of participants who are ADA total positive will be highlighted to explore the effect of ADA on PK of participants.

Pharmacokinetics

Plasma concentrations will be summarized descriptively for the PKAS in total at each analysis visit, using mean, SD, median, minimum, maximum, geometric mean, and coefficient of variation (CV).

Additional exploratory analysis may be performed after analysis of the data.

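### The only specified display of the effect of ADA on PK flags participants by whole-study ADA status rather than samples by concurrent status, so an ADA effect can be obscured

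*SAP*

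**What the plan says.** Protocol Section 7.7 says the plasma samples are taken "in order to evaluate the effect of ADA on the plasma concentrations of avacincaptad pegol". Protocol Section 7.6 sets the antibody schedule: "Assessments of anti-drug antibodies (ADA) will be performed at pre-dose at Month 1, Month 2, Month 4, Month 7, Month 13, and Month 18". Section 7.7 and the Study Assessments table (Section 3) place the PK samples at the same six visits.

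SAP Section 4.4 determines ADA status sample by sample, against the whole drug, against the aptamer, and as "ADA against Polyethylene glycol (PEG) for each ADA sample". For the link to PK it specifies one figure. The axis is by visit: "A plot of plasma concentrations vs. analysis visits (months) will be created". The ADA information on it is this: "Plasma concentrations of participants who are ADA total positive will be highlighted to explore the effect of ADA on PK of participants".

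SAP Table 1 defines the status behind the highlight. Total positive is "Total number of participants who are either with a negative baseline and at least one post-baseline positive ADA status, OR treatment boosted positive". Total negative is "Total number of participants who are not total positive". For a participant already positive at baseline, the footnote states that "a post-baseline titer value that is ≥ 4 times higher than the baseline is considered as treatment-boosted ADA".

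The PK table in the same section summarizes the whole PK analysis set by visit, without a split by ADA status. Further exploratory work is permitted but not described. SAP Section 2 plans no hypothesis tests.

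**The concern.** An antibody can change drug concentration only while it is present. The study collects what is needed to look at this directly, because each scheduled concentration has an ADA result from the same visit. The specified highlight does not use that pairing. It marks a participant on the basis of the whole study, so the highlighted set mixes concentrations from before and after antibody was first detected, and the SAP does not ask for the time of conversion to be shown.

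The unhighlighted set is also mixed. Baseline is the last value before the first ISEE2009 dose. A participant who developed antibody on active drug in ISEE2008 and is still positive at Month 1 therefore counts as baseline positive, and falls into total negative unless the titer rises 4-fold.

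What is at stake is the reading of a secondary endpoint. A plot in which highlighted and unhighlighted points overlap could be reported as showing no influence of ADA on PK, when both groups contain points of both kinds.

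**Working it through.** The documents give no ADA rate, effect size or power for this display, so there is no stated figure to reproduce. The check is a count on the sampling schedule.

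**Inputs**
- Paired ADA and PK visits: Months 1, 2, 4, 7, 13 and 18, so 6 pairs, 5 of them post-baseline (Protocol Sections 3, 7.6 and 7.7).
- Highlight rule: every concentration of a total-positive participant (SAP Section 4.4).
- Total positive: negative at baseline with any later positive, or treatment boosted (SAP Table 1).

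**Step 1. Converters who are negative at baseline.** Number the visits 1 to 6 and let the first positive fall at visit k (k = 2 to 6). All 6 concentrations are highlighted and k − 1 of them precede the first positive. This assumes that all six samples are available and that the participant stays positive.

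| First positive | Before first positive, all 6 | Before first positive, 5 post-baseline | At or after first positive, all 6 |
|---|---|---|---|
| Month 2 | 1/6 (17%) | 0/5 | 5/6 (83%) |
| Month 4 | 2/6 (33%) | 1/5 | 4/6 (67%) |
| Month 7 | 3/6 (50%) | 2/5 | 3/6 (50%) |
| Month 13 | 4/6 (67%) | 3/5 | 2/6 (33%) |
| Month 18 | 5/6 (83%) | 4/5 | 1/6 (17%) |

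The post-baseline column matters for Sham crossovers. Their Month 1 sample is drug-free and cannot inform an ADA effect. If positivity is transient, still more highlighted points are ADA-negative: a single positive visit gives 1 of 6.

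**Step 2. Treatment-boosted participants.** They are ADA-positive at baseline by definition, so they have no samples from before seroconversion. The counts in step 1 do not apply to them.

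**Step 3. Baseline-positive participants who are not boosted.** Take a participant who is positive at all six visits and whose titer never reaches 4 times baseline. ADA-positive concentrations: 6 of 6. Highlighted: 0 of 6. Compare the Month 18 converter in step 1: ADA-positive 1 of 6, highlighted 6 of 6. The documents do not say how many participants of either kind to expect.

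**Step 4. Reading by visit.** Assume, for illustration only, that first-positive visits are spread evenly over the five post-baseline visits. The share of highlighted converters already positive is then 0/5, 1/5, 2/5, 3/5, 4/5 and 5/5 at Months 1, 2, 4, 7, 13 and 18, that is 0%, 20%, 40%, 60%, 80% and 100%. Over all points the share is (5+4+3+2+1)/30 = 15/30 = 50%. Over post-baseline points it is 15/25 = 60%. Mixing is therefore heaviest at early visits and disappears by Month 18. For any one persistent converter it ends at the conversion visit.

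**The case against.** The strongest reply is that the figure is descriptive and keeps time on the axis. The highlight identifies a participant; the SAP does not say that each highlighted point is an ADA-positive sample. A persistent converter's concentrations at and after conversion appear at full size, and highlighting all of that person's values lets a reader find the earlier ones for comparison. Marking only positive samples would return the earlier values to the mass of points from about 280 participants. ADA results (SAP Section 4.4) and individual concentrations (Protocol Section 11.5) are both listed, so timing can be recovered by hand. That is practicable if positives are few, as the SAP's version history anticipates. Line and marker formats belong to the TLF specifications, which are not available here.

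Most of this stands. A reader might infer that any ADA effect is necessarily diluted, or attach a fold-reduction to it. The documents do not support that. Such a figure needs an average over all highlighted points, which the SAP does not plan, and an assumed effect size, which the documents do not give. The participant highlight should also be kept.

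Two things remain. The SAP text does not require the time of conversion or the concurrent ADA status to be shown on the one figure meant to address the question. And keeping the visit axis does nothing for baseline-positive, non-boosted participants, whose ADA-positive concentrations sit unmarked in the comparison set. Cross-reading two listings is a poor substitute for showing the contrast that the samples were taken to provide.

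**Conclusion.** The point holds as a limitation of one descriptive display. For converters who are negative at baseline, 1 to 5 of the 6 highlighted concentrations precede the first positive result, depending on when conversion occurs. ADA-positive concentrations of baseline-positive participants without a 4-fold titer rise are not highlighted, and this could include participants who seroconverted on active drug in ISEE2008. An ADA effect can be obscured when highlighted points are read as a group, or compared at visits before participants have converted. It is not diluted from this source when persistent converters are read visit by visit after conversion.

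The counts assume complete sampling and persistent positivity. The practical size depends on how many participants convert, when they convert, and how many are positive at Month 1, none of which the documents give. No test or estimate is affected, and the primary endpoint is untouched. This is a low-severity improvement, worth making because it costs almost nothing.

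**What to change.** In SAP Section 4.4:

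1. Keep total-positive participants identifiable on the plot, for example by joining each one's concentrations with a line.
2. Mark every plotted concentration, for all participants including those positive at baseline, by the ADA result of the same-visit sample. State which of the three ADA results (whole drug, aptamer, PEG) sets the marker.
3. Add a short table or listing of concentration by analysis visit and concurrent ADA status, with titer, showing values before and after the first positive for each converter.

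The cost is a few sentences of SAP text, one revised figure and one short table or listing. ADA and PK are already collected at the same visits, and SAP Table 4 already gives them common analysis windows, so no new data or visits are needed.

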10.5 Study Drug Discontinuation

In rare instances, it may be necessary for a subject to permanently discontinue study treatment before the planned study duration. If study treatment is permanently discontinued, the subject should, if at all possible, remain in the study to be evaluated for safety.

Subjects who discontinue study treatment or who decide they do not wish to participate in the study further should not be considered discontinued from the study unless they withdraw their consent and where possible, they should return for study visits and assessments according to the Study Assessments Chart, [Section 3](#).

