3.3 Pharmacokinetic Analysis Set

The pharmacokinetic analysis set (PKAS) consists of all treated participants with at least one valid plasma concentrations result. Additional participants may be excluded from the PKAS at the discretion of the pharmacokineticist.

The PKAS will be used for PK analysis.

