4 STATISTICAL ANALYSES

4.1 General Considerations

Continuous data will be summarized descriptively including the number of participants (n), mean, standard deviation (SD), median, minimum, Q1, Q3 and maximum. Categorical data will be summarized descriptively by frequencies and percentages. Percentages by categories will be based on the number of participants with no missing data, i.e., the percentages for the non-missing categories will add up to 100%. Participants with missing data are generally not included unless otherwise specified. When needed, the category of 'Missing' is created and the number of participants with missing data is presented.

All data summarization and analyses will be performed using SAS® Version 9.4 or higher on Red Hat Enterprise Linux. Specifications for table, figures, and data listing formats can be found in the Tables Listings Figures (TLF) specifications.

Summaries will be presented for the following cohorts unless otherwise specified:

- ACP EM to ACP EM, including all participants who received ACP every month (EM) through the Month 24 visit in the parent study ISEE2008 and enrolled in this study,
- ACP EM/EOM to ACP EM, including all participants who received ACP EM through the Month 11 visit and then randomized to ACP at Month 12 and administered ACP every other month (EOM) at Months 13, 15, 17, 19, 21, 23 in the parent study ISEE2008 and enrolled in this study,
- ACP to ACP EM, including all participants who received ACP EM through the Month 11 visit and then ACP EM or EOM through the Month 24 visit in the parent study ISEE2008 and enrolled in this study, which is the combination of the above two cohorts,
- Sham to ACP EM, including all participants who received Sham through the Month 23 visit in the parent study ISEE2008 and enrolled in this study,
- Total, including all participants who enrolled in this study regardless of the study drug and frequency they previously received in the parent study ISEE2008.

Baseline values will be defined as the last available value prior to the first administration of study drug in this study ISEE2009, unless otherwise specified.

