- Serious injection procedure related ocular TEAEs (SE),
- Serious non-ocular TEAEs,
- Serious Study drug related non-ocular TEAEs,
- Serious injection procedure related non-ocular TEAEs,
- Ocular TEAEs (SE) leading to withdrawal of study drug,
- Non-ocular TEAEs leading to withdrawal of study drug,
- Study drug related non-ocular TEAEs leading to withdrawal of study drug,
- Injection procedure related non-ocular TEAEs leading to withdrawal of study drug,
- Ocular TEAEs (FE) on and after the initiation of the ACP treatment on FE,
- Ocular TEAEs (FE) on and after the initiation of the Syfovre treatment on FE.

The number and percentage of participants with TEAEs, as classified by SOC and PT will be summarized by severity for each cohort. If a participant has multiple TEAEs with the same SOC or PT, but with differing severity, then the participant will be counted once with the worst severity grade. If severity is missing of the event, the participant will be counted under missing severity. Summaries will be provided for the following:

- TEAEs,
- Study drug related TEAEs,
- Injection procedure related TEAEs,

- Ocular TEAEs (SE),
- Study drug related ocular TEAEs (SE),
- Injection procedure related ocular TEAEs (SE).

All AEs, including non-TEAEs, serious AEs, AEs leading to withdrawal of study drug and AEs leading to death will be listed.

The listings will include the subject identifier, age, sex, verbatim term, SOC, PT, eye (N/A / OD / OS / OU), serious (yes/no), date of onset, relative study day of onset, onset timing, duration of the event (or continuing), severity (mild/moderate/severe), causality (relationship to study drug/injection procedure), action taken (study drug permanently discontinued: yes/no), treatment required (yes/no), and outcome (resolved/not resolved/fatal).

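### Plasma PK is tabulated only in total, so the Month 1 summary (and possibly Month 2) mixes drug-free Sham crossovers with ACP-experienced participants, and no below-quantification rule supports the planned geometric mean

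*SAP*

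**What the plan says.** The SAP's general rule (4.1) is "Summaries will be presented for the following cohorts unless otherwise specified", followed by the prior-treatment cohorts (ACP monthly, ACP monthly then every other month, the two combined, and Sham) and a Total. For PK, SAP 4.4 specifies otherwise: "Plasma concentrations will be summarized descriptively for the PKAS in total at each analysis visit". The listed statistics include the mean, the median and the geometric mean. The SAP text gives no rule for zero or below-quantification values.

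The PK analysis set (SAP 3.3) "consists of all treated participants with at least one valid plasma concentrations result". The pharmacokineticist may remove further participants, without stated criteria.

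On what goes into the pool:

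- **Sham crossovers.** Protocol 7.6 takes their Month 1 pre-dose immunogenicity sample "to capture a drug-free baseline". The footnote to the schedule in Protocol 3 says the same of the Month 1 immunogenicity and PK samples.
- **ACP-experienced participants.** They come from monthly or every-other-month dosing (SAP 4.1) and may enrol up to 90 days after parent Month 24 (Protocol 10.1).
- **Off-drug participants.** Under Protocol 10.5, after permanent discontinuation "the subject should, if at all possible, remain in the study to be evaluated for safety", with visits following the schedule where possible.
- **Fellow-eye ACP.** SAP 4.6.1 plans a table of "Ocular TEAEs (FE) on and after the initiation of the ACP treatment on FE". The only handling rule for ACP-treated fellow eyes is in the safety section (SAP 4.6), not under PK.

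Protocol 7.7 gives the purpose of sampling: "in order to evaluate the effect of ADA on the plasma concentrations of avacincaptad pegol". SAP 4.4 adds a plot of concentration by visit with ADA total positive participants highlighted.

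**The concern.** Prior exposure largely determines the early plasma values, and PK is where the SAP drops the prior-exposure cohorts. A single Month 1 column averages a group with no drug in plasma and a group with whatever remains from the parent study. The result describes neither. If about half the pool is drug-free, the median also falls near the boundary between the groups and says little.

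The geometric mean is prespecified for every visit, including the one at which a whole cohort is drug-free by design. It either cannot be computed or takes a value fixed by a programming choice made outside the SAP.

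At later visits, the ADA–PK question is exposed to unmarked samples. A low concentration in an ADA-positive participant who has stopped drug could be read as an ADA effect. A participant also receiving ACP in the fellow eye could hide one.

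**Working it through.** **1. Which samples fall in which visit.** Rebuilding SAP Table 4, scheduled day = 30.4375 × (month − 1), rounded, gives 30, 91, 183, 365 and 517. Lower bound = day − half the gap to the previous scheduled visit:

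- Month 4: 91 − 61/2 = 60.5, rounded to 61
- Month 7: 183 − 92/2 = 137
- Month 13: 365 − 182/2 = 274
- Month 18: 517 − 152/2 = 441

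All match the table. The windows depend on study day alone, not on whether the participant is still on drug.

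**2. Month 1 mean.** Let s be the Sham share, with Sham values taken as 0. Pooled mean ÷ ACP-cohort mean = 1 − s. The share in ISEE2009 is not given. The parent study treated 225 on ACP and 222 on Sham, so 222/447 = 49.7%. I assume 40% to 60%.

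| s | pooled ÷ ACP mean |
|---|---|
| 0.40 | 0.60 |
| 0.50 | 0.50 |
| 0.60 | 0.40 |

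The ratio does not depend on how much drug remains in the ACP cohorts. The absolute gap does, and it is small if little remains.

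**3. Month 1 geometric mean.** With zeros it is undefined. If drug-free values are replaced by a fraction e of the ACP-cohort geometric mean, pooled ÷ ACP = e^s. At s = 0.5:

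- e = 0.5: 0.71
- e = 0.1: 0.32
- e = 0.01: 0.10

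The answer moves sevenfold (0.71/0.10) on the substitution alone.

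**4. Months 2 to 7, Sham crossovers on monthly dosing.** In a one-compartment approximation, the pre-dose level after n monthly doses, as a fraction of steady state, is 1 − 2^(−30.4375 n / h). The plasma half-life h is not in the documents; I assume 7 to 30 days.

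| Visit (n doses) | h = 30 days | h = 7 days |
|---|---|---|
| Month 2 (1) | 0.505 | 0.951 |
| Month 4 (3) | 0.879 | 1.000 |
| Month 7 (6) | 0.985 | 1.000 |

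At Month 2 with s = 0.5, and ACP-experienced participants at steady state, the pooled mean is 1 − 0.5 × (1 − 0.505) = 0.75 up to 1 − 0.5 × (1 − 0.951) = 0.98 of theirs. That is the wider end of the gap, because a long enrolment delay lowers the ACP cohorts too.

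**5. Rise from Month 1 to Month 4.** Let r be the ACP-experienced mean at Month 1 as a fraction of the common Month 4 level. The Sham cohort's part of the pooled rise is s / [s + (1 − s)(1 − r)]. With s = 0.4 and r = 0 it is 0.40; with r = 1 it is 1. After every-other-month dosing that ended at parent Month 23, enrolment 90 days after Month 24 puts Month 1 about 30 + 90 = 120 days after the last dose. The level is then 2^(−90/h) of its 30-day value: 0.125 for h = 30 and about 0.0001 for h = 7. So r could lie well below 1.

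**6. Later visits.** Let d be the share off drug (level 0) and b the share dosed in both eyes (level 2, if both eyes contribute equally). Pooled mean ÷ one-eye monthly level = 1 − d + b. The documents give neither share. For 0 to 20% each, the range is 0.80 (d = 0.2, b = 0) to 1.20 (d = 0, b = 0.2). At 10% each it is 1.00, while the geometric mean ratio, e^0.1 × 2^0.1, is 1.00, 0.85 or 0.68 for e = 0.5, 0.1 or 0.01.

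**The case against.** The strongest reply is that every participant receives the same 2 mg monthly regimen in this study and, Month 18 apart, is sampled before that visit's injection. A reader might infer from the pooling that the summary describes no dosing state at any visit. The documents do not support that. Under the half-lives assumed, former Sham participants are at 88% to 100% of steady state by Month 4 and at least 98.5% by Month 7, so pooling on-drug participants by prior arm is reasonable for four of the six sampling visits.

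Three further inferences go too far:

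- **That a rise from Month 1 to Month 4 would be mostly the Sham cohort starting drug.** This needs ACP-experienced participants to be near their monthly level at Month 1. With every-other-month dosing and an enrolment gap of up to 90 days, that cannot be assumed (step 5).
- **That fellow-eye dosing inflates the mean, or stopping drug dilutes it, to a material degree.** No shares are given, Protocol 10.5 describes permanent discontinuation as rare, and the two effects oppose each other.
- **That the ADA–PK plot inherits the dilution of the pooled mean.** It reads as a plot of participants' own values. Its gap is the lack of marks for off-drug and fellow-eye-ACP samples.

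There are also mitigations. Protocol 11.5 promises an individual listing, SAP 3.3 allows exclusions from the analysis set, SAP 4.4 allows further exploratory analysis, and SAP 2 rules out hypothesis tests. A below-quantification rule may sit in the separate table specifications, which are not available here. These points lower the severity. They do not repair the Month 1 column: a listing does not correct a summary table, and exclusion of participants without criteria does not replace a rule for samples.

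**Conclusion.** The point stands for Month 1 and possibly Month 2. Followed as written, SAP 4.4 gives a Month 1 mean of about half the ACP-cohort mean (0.60 to 0.40 for an assumed Sham share of 40% to 60%, Sham values taken as zero). The geometric mean at that visit is either undefined or governed by a rule absent from the SAP. At Month 2 the cohorts may still differ, with the first-dose level at 51% to 95% of steady state for assumed half-lives of 30 to 7 days. From about Month 4, pooling by prior arm is acceptable for participants on drug. What remains there is that off-drug and fellow-eye-ACP samples are unmarked, an effect whose size and sign cannot be determined from the documents.

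Severity is minor to moderate: PK is a descriptive secondary endpoint with no inference attached.

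**What to change.** In SAP 4.4:

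1. Summarise plasma concentrations by the existing SAP 4.1 cohorts plus Total, at minimum at Months 1 and 2.
2. State how below-quantification values enter the mean and the geometric mean, and report no geometric mean for the drug-free Sham samples at Month 1.
3. Flag samples taken after stopping study drug, or after the start of fellow-eye ACP, in the concentration listing and the ADA–PK plot. Keep them in the main summary and add a supportive summary without them. Removing fellow-eye-ACP samples from the main table could hide the highest systemic exposures in a safety study. A fixed days-since-dose window has no basis in the documents and could drop many ACP-experienced Month 1 samples.

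The cost is SAP wording, a few more table columns with smaller n in each, and one supportive table. No new data are needed.
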